Can *Lactobacillus acidophilus* decrease the risk of postmenopausal osteoporosis in women?

Short Description

Background

The current recommendations for treating bone diseases are estrogen therapy and pharmacological agents. However, those treatments increase the risk of cancers and are not prescribed for long-term use. *Lactobacillus acidophilus* in ovariectomized mice could inhibit osteoclastogenic cells and promote anti-osteoclastogenic cells.

Aim of study

This study aims to evaluate the effect of *L. acidophilus* supplementation on calcium status and bone densitometry in postmenopausal women in a randomized, double-blind placebo-controlled study.

Study design

This study has three steps; namely, **1st step** is to prepare the diet supplementation of probiotics (*L. acidophilus* 1×10^9 CFU). **2nd step** is to perform the randomized, double-blind placebo-controlled clinical trial. **3rd step** is to analyze the effects of *L. acidophilus* in postmenopausal women.

Methods & Analysis

60 women of postmenopausal osteoporosis will be recruited by following inclusion and exclusion criteria. Participants will be randomized and divided into two groups to take a capsule containing probiotics and a placebo for 12 weeks. Before and after the intervention, several parameters will be conducted, such as the bone turnover and hormones parameter in blood using ELISA, the calcium mineralization in hair sample using AAS, the bone densitometry analysis in bone using DXA.

Research Design

Study settings

This study will be conducted within two (2) years for research activity and one (1) year for the publication period. There are three steps within this study; namely, **1st step** is to prepare the sample of *L. acidophilus* as diet supplementation. Probiotic capsules will contain *L. acidophilus* 1×10^9 CFU. **2nd step** is to perform the randomized, double-blind placebo-controlled clinical trial of *L. acidophilus* supplementation for twelve weeks (Figure 1). **3rd step** is to analyze the effects of *L. acidophilus* in postmenopausal women.

[figure not shown]

Figure 1. Flow diagram of patient recruitment

Eligibility criteria (inclusion, exclusion criteria)

The inclusion and exclusion criteria are provided in figure 2. Informed consent should be obtained from all patients, and the patients will be asked to notify the researchers if medical changes occurred during the intervention.

Inclusion criteria

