
 • All female participants who accepted bone densitometry measurement • Women aged 40-55 years with an intact uterus • BMI of < 34.0 kg/m², and > 7 moderate-to-severe hot flushes daily • Women will be considered to be postmenopausal if they had had either > 12 months of spontaneous amenorrhea or > 6 months of spontaneous amenorrhea with serum follicle-stimulating hormone levels of > 40 mIU/mL
Exclusion criteria

 • Diabetes • Secondary obesity • Gastrointestinal diseases • Use of dietary supplements, including calcium, in the three months before enrollment • Pharmacotherapy of lipid disorders or hypertension in the three months before enrollment • Clinically significant acute inflammatory process • Antibiotics intake within the month before enrollment • Participation in a body mass management study • The use of drugs known to modify body mass or food intake • Abuse of alcohol, nicotine, or drugs • Hormone replacement therapy • Vegetarian diet • Use of probiotic enriched or prebiotic enriched products in the three weeks before enrollment • Consumption of products with high dietary fiber content, or consumption of more than 400 g of fermented food a day • Diagnosed osteoporosis

Figure 2. Inclusion and Exclusion criteria

Interventions or exposures

[figure not shown]

Figure 3. Diagram of the intervention period

The intervention period during this study can be seen in figure 3. The diet intervention in this experiment will be performed for 12 weeks, as Ahn et al. (2019) described. Two groups will be designated in this study. Group 1 is the placebo group that will receive a capsule that consists of the excipient. The excipient will be composed of maize starch and maltodextrins (Skrypnik et al., 2019). Group 2 is the probiotic group that will receive a diet capsule consisting of *Lactobacillus acidophilus* with a dose of 1×10^9 CFU with the excipient described by Hosseini et al. (2019). In addition, it is essential to deliver self-administration of probiotic agents orally in the morning with fasting conditions to evaluate probiotic effectiveness. Subsequently, patients will be asked to keep the diet in refrigerated condition (2-7 °C).

Primary endpoints

This study will consider the change from baseline in the frequency and severity of hot flushes as primary endpoints.

Secondary endpoints

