Meanwhile, the health-related quality of life, sleep, satisfaction with treatment, and cumulative amenorrhea and breast pain will be considered as secondary endpoints.

Sample size calculation

To calculate sample size, this study refers to the Soleimani et al. (2017) study. Using a formula suggested for clinical trials, having 25 participants in each group will be considered adequate

while considering a type I error (a) of 0.05 and type II error (b) of 0.20 (power $1 - \beta = 80\%$), with 1.61 as the SD and 1.30 as the mean distinction of CTX for markers of bone resorption and BSAP for marker of bone formation as the key variable. By assuming five dropouts in each group, the final sample size will be 30 participants in each group.

Methods assignment of interventions

Randomization will be performed using a computerized random number generator, which generated the random sequence based on simple randomization. All subjects will be identified by a trial identification number and assigned a treatment code. The researchers and participants will be blinded to the treatment code until the end of the study when data will be collected and evaluated. The groups will be decided after the completion of the data analysis.

Variable assessment

All information is containing 3 days dietary records, body composition measurement, and fasting blood samples will be collected at the beginning and end of the study. DIETA 6.0 and 5D computer program by Instytut Żywości i Żywienia, Poland will be used for analyzing 3 days averages of macronutrients and micronutrient intakes. A validated questionnaire obtains personal and demographic information. Anthropometric measurements will be measured using body composition analysis.

Biomarkers of bone turnover and hormones

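### The readable protocol describes no measurement for any of its declared primary or secondary endpoints, so the change from baseline in hot flushes would have no data behind it

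*Protocol*

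**What the plan says.** **Endpoints.** The Primary endpoints section names the "change from baseline in the frequency and severity of hot flushes as primary endpoints". The Secondary endpoints section adds that "health-related quality of life, sleep, satisfaction with treatment, and cumulative amenorrhea and breast pain will be considered as secondary endpoints".

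**Entry criterion.** Figure 2 (Inclusion criteria) requires "> 7 moderate-to-severe hot flushes daily".

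**Assessments.** Variable assessment states: "All information is containing 3 days dietary records, body composition measurement, and fasting blood samples will be collected at the beginning and end". The same section mentions one questionnaire, for personal and demographic information. The sections that follow describe eight named blood markers, hair and serum calcium, and bone densitometry by DXA. The Methods & Analysis summary is of the same kind: "Before and after the intervention, several parameters will be conducted, such as the bone turnover and hormones parameter in blood using ELISA", followed by hair calcium and DXA.

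**Aim and sample size.** The stated aim concerns calcium status and bone densitometry. The sample size rests on CTX and BSAP.

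**The concern.** A change from baseline needs one value before the first capsule and one at the end of the 12 weeks. The protocol describes its laboratory and imaging work closely, down to the length of the hair strand and the kind of shampoo. For hot flushes it gives no diary, count, severity grade, recall window or collection time. For quality of life, sleep, satisfaction, amenorrhea and breast pain it gives no instrument or record.

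If sites collect what is described and nothing more, the trial ends without data on its declared primary endpoints. An analysis plan cannot repair this, because it can only say how collected data are used. Asking women at week 12 to recall their flushes from 12 weeks before would give a recalled baseline, not a measured one.

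**Working it through.** The check sets each declared endpoint beside every assessment that the readable protocol describes.

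**Described assessments**
- Variable assessment: 3-day dietary records, body composition, fasting blood, and a questionnaire for personal and demographic data.
- Biomarkers of bone turnover and hormones: CTX, TRAP5b, BSAP, PINP, adiponectin, IGF-1, PTH and cortisol (8 markers).
- Hair sample and Calcium analysis: hair and serum calcium.
- Bone densitometry analysis: DXA.

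**Comparison**

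| Declared endpoint | Role | Described measurement |
|---|---|---|
| Hot-flush frequency | Primary | None |
| Hot-flush severity | Primary | None |
| Health-related quality of life | Secondary | None |
| Sleep | Secondary | None |
| Satisfaction with treatment | Secondary | None |
| Cumulative amenorrhea | Secondary | None |
| Breast pain | Secondary | None |

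Count: 0 of 2 primary and 0 of 5 secondary, so 0 of 7. As measured outcomes, hot flushes appear only in the inclusion criterion and in the primary endpoint sentence.

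**Entry criterion.** It needs both a count per day and a severity grade. The text gives no method for either.

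**Sample size.** This shows which endpoint the trial was sized for. Inputs from Sample size calculation: SD 1.61, difference 1.30, alpha 0.05, power 80%, sizing variables CTX and BSAP. Sidedness is not stated; two-sided is assumed first.

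- n per group = 2 × (1.96 + 0.84)² × (1.61 / 1.30)² = 2 × 7.85 × 1.534 = 24.1, rounded up to 25. This reproduces the protocol's figure. The one-sided version gives 19 and does not fit.
- The two-sided t-test gives 25.07 per group, with power 79.9% at 25, which is no material difference.
- With dropouts: 25 + 5 = 30 per group, so 60 in total, as stated.

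The calculation is therefore sound on its own terms, but only for CTX/BSAP. The protocol gives no SD or target difference for hot flushes, so power for the declared primary endpoints cannot be computed. All that can be said is the standardised difference detectable with 80% power at two-sided 0.05, whatever the endpoint (normal approximation):

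- 25 per group: (1.96 + 0.84) × √(2/25) = 0.79 SD
- 30 per group: (1.96 + 0.84) × √(2/30) = 0.72 SD

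**The case against.** **Unseen figures.** Figure 3, the diagram of the intervention period, is not shown, and neither is Figure 1. Figure 3 could carry a symptom assessment. This stands, and it limits the finding to the readable text.

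**The list may not be complete.** The sentence in Variable assessment omits hair sampling and DXA, which other sections require, and the summary presents its parameters as examples. So that sentence alone cannot show that nothing else is collected. This also stands. The finding rests instead on all the assessment sections together, none of which describes a symptom measurement.

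**Eligibility.** A reader might infer that the hot-flush criterion cannot be verified, or that entry rests on unrecorded recall. The documents do not support that. Variable assessment covers the beginning and end of the study and does not set out screening. The FSH threshold among the entry criteria is also absent from the listed assays, so absence there does not show that a criterion goes unchecked. Ascertainment Feasibility says the department receives patients who meet the criteria, which presupposes some check. What remains is that the counting method is not stated.

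**The endpoints may be the error.** The title, aim, sample size and assays all concern bone and calcium, and the endpoint sentences are the outlier. If the sponsor declares the measured outcomes as endpoints, the measurement gap for the seven items disappears. This is a fair point about the order of the repair, and it is why reconciliation comes first. It does not remove the conflict in the current text.

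**Reporting of medical changes.** Patients are asked to tell the researchers about medical changes during the intervention. That is unscheduled reporting and supplies neither a baseline nor a week-12 value.

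**Conclusion.** The concern holds for the readable text. None of the 7 declared endpoints has a described measurement, and the method for the hot-flush entry count is not stated. Followed as described, the trial would reach week 12 with no baseline or final value for its declared primary endpoints in any of the 60 women, and the baseline could not be recovered afterwards. This needs correction before randomization starts.

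The conclusion assumes that the unseen Figures 1 and 3 add no symptom assessment and that sites collect only what the text describes. It would be too strong to say that the trial's schedule as a whole is known to omit these endpoints. No corrected sample size follows, since the protocol gives no figures for hot flushes.

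**What to change.** Before the first participant is randomized, reconcile the endpoints with the aim, the described assessments and the sample size variable (CTX/BSAP). There are two routes:

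1. **Declare what is already measured.** Make the bone and calcium outcomes the endpoints, and delete the symptom endpoints that will not be measured. This costs protocol wording only.
2. **Keep the symptom endpoints and measure them.** Add to Variable assessment a hot-flush diary (count and severity) in both arms, before randomization and at the end of week 12. Seven days each is a suggestion, not a figure from the protocol. The first diary can also document the entry count. Collect quality of life, sleep, breast pain and a bleeding/amenorrhea record at the same two time points, and satisfaction at week 12. State that 25 evaluable and 30 randomized per group were derived for CTX/BSAP only. The cost is a small participant burden and a short run-in before randomization.

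On either route, state how the hot-flush entry count is obtained for as long as that criterion is kept. If Figure 3 already shows such assessments, repeat them in the text.
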